9.2.3 Key Secondary Efficacy Analyses

The key multiplicity adjusted secondary efficacy endpoints at Week 14 are:

1. Change from Baseline in Ankylosing Spondylitis Disease Activity Score (ASDAS(CRP));
2. Change from Baseline in MRI Spondyloarthritis Research Consortium of Canada (SPARCC) score (Spine);

3. Proportion of subjects with BASDAI 50 response (defined as 50% improvement in the Bath AS Disease Activity Index);
4. Change from Baseline in AS QoL;
5. Proportion of subjects with ASAS partial remission (PR) (defined as an absolute score of ≤ 2 units for each of the four domains identified in ASAS 40);
6. Change from Baseline in BASFI;
7. Change from Baseline in BASMI_{lin};
8. Change from Baseline in MASES (for subjects with baseline enthesitis);
9. Change from Baseline in WPAI (the overall work impairment due to SpA);
10. Change from Baseline in ASAS HI.

Additional key secondary endpoints are:

- ASAS 20 response at Week 14.
- Change from Baseline in MRI SPARCC score (SI joints) at Week 14.

For binary endpoints, frequencies and percentages will be reported for each randomized treatment group. The primary estimand is the same as that for the primary efficacy endpoint as defined in Section 9.2.1, except for the definition of the efficacy measurement. NRI data handling will be used to analyze the primary estimand.

Supplementary analysis using AO data handling will also be conducted. The corresponding supplementary estimand is the same as defined in Section 9.2.2 except for the definition of the efficacy measurement. To explore various missing data assumptions including missing not at random (MNAR), tipping point analysis will also be conducted for ASAS 20 at Week 14 and details of the analysis are outlined in Appendix E.

Point estimate and 95% CI using normal approximation will be provided for the response rate for each randomized treatment group. Treatment comparisons will be made between

upadacitinib and the placebo group using the Cochran-Mantel-Haenszel. The CMH test adjusts for the main stratification factor of hsCRP level (\leq ULN vs. $>$ ULN). Point estimate, 95% CI using normal approximation and the p-value for the treatment difference will be presented.

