Appendix E. Tipping Point Analysis

Tipping Point Analysis for binary endpoint ASAS40 (and ASAS 20)

To assess the robustness of the primary analysis using NRI data handling, tipping point analysis is conducted on the primary endpoint ASAS40. The analysis is conducted using As Observed data handling.

Let M_1 be the number of subjects missing ASAS40 status in the placebo group, and let M_2 be the number of subjects missing ASAS40 status in the upadacitinib group. Let X_1 be the number of subjects imputed as ASAS40 responders out of the M_1 subjects with missing ASAS40 status in the placebo group – the rest are imputed as non-responders. X_1 can take values from 0 to M_1 . Similarly define X_2 . Given each pair of (X_1, X_2) , we can obtain the p-value for the treatment comparison of upadacitinib versus placebo using the combined observed data and imputed data for each treatment group. If one pair of parameters are found to just reverse the study conclusion, in terms of p-value larger than 0.05 (the original p-value < 0.05), then these parameters are called the tipping point.

Tipping Point Analysis for Continuous Endpoints

To assess the impact of potential departures from the missing-at-random assumption, tipping point analyses are conducted as a sensitivity check for change from baseline in ranked secondary endpoints at the primary time point. The tipping point analyses are two-dimensional, i.e., assumptions about the missing outcomes on the upadacitinib treatment group and the placebo group are allowed to vary independently. In addition, the focus is on scenarios where missing outcomes on upadacitinib are worse than the imputed values on upadacitinib, while missing outcomes on placebo are better than the imputed values on placebo. Missing values are first imputed via multiple imputation (MI) under MAR, and then a shift parameter is applied to the imputed values (a different shift parameter may be specified for each treatment group). (The MI imputation is performed upon AO data). This is implemented by PROC MI using the MNAR statement. For a given pair of shift parameters, the SAS code example is as follows:

```
PROC MI DATA=DATA WIDE OUT=OUTMI NIMPUTE=5 SEED=12345
  MINMAXITER=1000;
  CLASS TRTP COVCAT;
  MONOTONE;
  VAR TRTP COVCON COVCAT WEEK_2 WEEK_4 WEEK_8 WEEK_12;
  MONOTONE REG( WEEK_2 = TRTP COVCON COVCAT );
  MONOTONE REG( WEEK_4 = TRTP WEEK_2 COVCON COVCAT );
  MONOTONE REG( WEEK_8 = TRTP WEEK_2 WEEK_4 COVCON COVCAT );

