  MONOTONE REG( WEEK_12 = TRTP WEEK_2 WEEK_4 WEEK_8 COVCON COVCAT );
  MNAR ADJUST (WEEK_12 / SHIFT=&SJ1 ADJUSTOBS=(TRTP='PLACEBO'));
  MNAR ADJUST (WEEK_12 / SHIFT=&SJ2 ADJUSTOBS=(TRTP='UPA 15MG'));
RUN;
```

Note: The input dataset is the same as that used for MI analysis. The macro variables SJ1 and SJ2 denote the shift parameters for the placebo group and the upadacitinib group respectively.

In cases where the shifted values are smaller than the minimum or larger than maximum value of the endpoints, (i.e., out of range), the minimum or maximum value is used in further analysis steps. For each pair of shift parameters, the same analysis as the primary MI analysis is then conducted to obtain the p-values for the upadacitinib treatment group versus the placebo group. If one pair of shift parameters are found to just reverse the study conclusion, in terms of p-value larger than 0.05 (the original p-value < 0.05), then the shift parameters are identified as the tipping point. The results for a grid of shift parameter combinations are provided in tabular format.

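### SAP Appendix E does not match the Week 14 analyses it is meant to stress: the example imputation code stops at Week 12, and the ASAS40 grid meant to test NRI lets drug discontinuers count as responders

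*SAP*

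**What the plan says.** **Continuous endpoints.** Appendix E states that "tipping point analyses are conducted as a sensitivity check for change from baseline in ranked secondary endpoints at the primary time point". SAP 9.2.3 fixes that time point: "The key multiplicity adjusted secondary efficacy endpoints at Week 14 are", followed by the ranked list. The imputation is specified only through code, introduced by "For a given pair of shift parameters, the SAS code example is as follows". Its variable list is "VAR TRTP COVCON COVCAT WEEK_2 WEEK_4 WEEK_8 WEEK_12", its last regression is for Week 12, and both shift statements act on Week 12; the placebo one begins "MNAR ADJUST (WEEK_12 / SHIFT=&SJ1 ADJUSTOBS=(TRTP='PLACEBO". On data, the appendix says "The MI imputation is performed upon AO data", and the note to the code adds "The input dataset is the same as that used for MI analysis". For each pair of shifts, "the same analysis as the primary MI analysis is then conducted".

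**Binary endpoints.** Appendix E gives the purpose of the ASAS40 grid as assessing the robustness of the NRI primary analysis, then says that it runs on As Observed (AO) data. Any number of the subjects with missing status in an arm, from none to all, may be imputed as responders. SAP 9.2.3 extends this to ASAS20.

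**The analyses being checked.** SAP 9.2.1 defines the primary estimand as a composite: ASAS40 response at Week 14 without stopping study drug by Week 14. It splits non-responders into (1) drug discontinuers, (2) subjects on drug with Week 14 missing and (3) observed failures on drug. Under SAP 9.1.2, NRI makes every discontinuer a non-responder, AO uses all observed data regardless of discontinuation, and the MMRM excludes post-discontinuation data. Protocol 5.4.1 asks discontinuers to keep attending scheduled visits.

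**The concern.** A tipping point analysis should vary what is unknown and hold the estimand fixed. For the composite estimand, a discontinuer's failure is part of the definition and is not a missing-data assumption. Only category 2 subjects have an uncertain status. An AO grid departs from this twice: observed off-drug responders stay responders in every cell, and discontinuers with missing status may be imputed as responders. Its (0,0) cell then need not equal the NRI result that it is said to test.

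For the continuous endpoints, a programmer following the code would impute and shift a visit that is not the endpoint visit, and would find no named model to fit afterwards.

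This is the only missing-not-at-random check that SAP 9.2.2 names for the primary endpoint, so a wrong reading of robustness has no other planned check of that kind to correct it.

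**Working it through.** **Part (a): visits in the code against visits scheduled (SAP 5.2, Tables 1 and 3 to 6)**

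| Ranked continuous endpoint | Post-baseline Period 1 visits | Week 12? |
|---|---|---|
| ASDAS, BASFI | 2, 4, 8, 12, 14 | yes |
| ASAS HI | 2, 4, 8, 14 | no |
| AS QoL, MASES | 4, 8, 14 | no |
| WPAI, BASMI, spine SPARCC | 14 only | no |

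The code contains Week 14 for 0 of 8 endpoints. Week 12 exists for 2 of 8 and Week 2 for 3 of 8. For the last row the code contains no post-baseline visit at which the endpoint is scheduled. The models actually defined in SAP 9.2.3 are an MMRM and an AO ANCOVA; neither is an MI analysis. The MI uses AO data while the MMRM drops post-discontinuation data, so as written the check relates to the AO estimand rather than the MMRM one. No p-value effect is claimed for part (a).

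**Part (b): illustration**

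*Design figure first.* SAP 4.3: 20% v 46%, two-sided 0.05, 90% power, 10% dropout, total 170. The two-proportion formula gives 67 per arm, or 75 with continuity correction. Then 75/0.9 = 83.3, so 84 per arm and 168 in total, which agrees with 170. The design figures are not in dispute.

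*Inputs from the documents:* 85 per arm; placebo 20%, i.e. 17/85; 10% dropout, about 8 per arm. *Assumed, because the documents give no such counts:* upadacitinib NRI responders 34, 36 or 39 (39/85 is the design 46%); 8 missing placebo statuses; the number of discontinuers among them; the number of off-drug responders. No missing upadacitinib subject is imputed as a responder (X2=0).

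*Test:* single-stratum CMH, Q = (a − E)²/V on 1 df, where a is the upadacitinib responders, t all responders, N=170, E = t/2 and V = 85·85·t(N−t)/(N²(N−1)). Example, 36 v 24: t=60, E=30, V = 85·85·60·110/(170²·169) = 9.763, Q = 36/9.763 = 3.687, p = 0.055. The tip is the smallest X1 (missing placebo subjects imputed as responders) with p>0.05.

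*Starting NRI results:* 34 v 17, p=0.0046; 36 v 17, p=0.0017; 39 v 17, p=0.0003.

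*The AO grid can make NRI look too fragile.* The composite-consistent grid stops at X1 = 8 − c, where c of the 8 missing had stopped drug.
- 36 v 17: X1=6 gives p=0.037 and X1=7 gives p=0.055. AO tips at 7. With c≥2 the composite grid cannot pass 6 and never tips.
- 34 v 17: X1=4 gives p=0.034 and X1=5 gives p=0.051. AO tips at 5. With c≥4 the composite grid never tips.
- 39 v 17 (design rate): the composite grid never tips, even with c=0 (39 v 25, p=0.027). With two off-drug placebo responders, AO tips at X1=8 (39 v 17+2+8=27, p=0.060). With 9 missing, one off-drug placebo responder is enough (17+1+9=27).

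*It can also make NRI look too robust.*
- 36/85: one off-drug upadacitinib responder moves the AO tip from 7 to 8 (37 v 24, p=0.038; 37 v 25, p=0.057). Two remove it (38 v 25, p=0.040).
- 34/85: one, two and three such responders move the tip from 5 to 6, 7 and 8; four remove it.

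*Stratified check* (hsCRP above-ULN share 50–80%, response odds ratio between strata 1–3, both assumed): 39 v 27 gives p=0.052–0.061 and 39 v 25 gives p=0.023–0.028. The tip points in the off-drug upadacitinib cases stay the same or come one step later; a tip at 8 can disappear.

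**The case against.** The code is labelled an example, the text around it points to Week 14, and nothing shows that Week 12 was actually shifted. That stands: part (a) alone is a minor text-code correction, probably template carry-over.

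For part (b), SAP 9.2.2 lists the tipping point as supplementary, Appendix E declares the AO handling openly, and an AO grid is a valid check of the AO estimand in SAP 9.2.2. Relabelling the purpose sentence would remove the contradiction. It would also leave the NRI result with no missing-not-at-random check of its own.

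The planned outputs allow some reconstruction. The category 2 count bounds the relevant part of the grid, and AO responders minus NRI responders shows the off-drug responders in each arm. With no off-drug responders, the composite grid is simply a subset of the AO grid. But where off-drug upadacitinib responders exist, the cells with fewer upadacitinib responders are absent from the AO grid and cannot be recovered from it. A reader should not have to rebuild the check in any case.

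The examples rest on chosen counts. At the design rate with 8 missing and no off-drug responders, neither grid tips; the tip there needs two off-drug placebo responders, all 8 missing placebo subjects responding, and X2=0. That is a far edge of the grid. The objection limits the likely size of the effect but does not make the rule fit its stated purpose.

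**Conclusion.** The concern holds in both parts and should be fixed, mainly because of part (b). Followed literally, Appendix E imputes and shifts the wrong visit for the continuous endpoints and leaves the analysis model unnamed. For ASAS40 and ASAS20 it does not hold the primary estimand fixed, so its verdict on NRI can err in either direction, by one or more steps of X1 or by creating or removing a tip altogether.

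The size in this trial cannot be taken from the documents, which give neither the off-drug responders nor the discontinuers among the missing; the figures above are illustrations. If there are no off-drug responders and every missing subject is still on drug, the two grids are identical. Both parts concern supplementary analyses: the primary estimate, its p-value and type I error control do not change.

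**What to change.** **Continuous.** Impute and shift Week 14 using each endpoint's own schedule (baseline and Week 14 only for WPAI, BASMI and spine SPARCC). Replace the reference to a primary MI analysis with a named model: Week 14 ANCOVA with treatment, hsCRP stratum and baseline, combined by Rubin's rules. Keep MASES to subjects with baseline enthesitis (SAP 9.2.3). Do not impute WPAI overall work impairment where SAP 9.4.10 sets it to missing because the subject is not employed. Label the check as stressing the AO estimand or, if it is meant to support the MMRM, set post-discontinuation values to missing first.

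**Binary.** Add a grid that counts every study-drug discontinuer as a non-responder, observed or missing, and varies only category 2 subjects. Its (0,0) cell then equals the NRI result by construction. Keep the AO grid, relabelled as a check of the supplementary AO estimand.

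**Reporting.** SAP 11.0 places the Week 14 lock in February 2019. State which visit, data set and model were run then, re-run where they differ, and label any new or repeated analysis post hoc.

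**Cost.** A few lines of Appendix E, one small grid per binary endpoint, a statement of what was run, and a re-run of supplementary analyses only if needed. No new data.

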Appendix F. Geographic Region

Below table lists the countries considered for each geographic region.

Geographic Region	Countries
Asia	Japan, South Korea
Eastern Europe	Croatia, Czech Republic, Hungary, Poland
North America	Canada, United States
Other	Australia, New Zealand
Western Europe	Belgium, Denmark, Finland, France, Germany, Netherlands, Portugal, Spain Sweden, United Kingdom

Appendix G. Low Dose CT Imaging

Per study protocol, subjects enrolled into Study M16-098 can choose to enroll into a sub-study in which low dose CT imaging of the spine is performed. The analysis population for low dose CT includes all the subjects who consented to the sub-study, were randomized, with at least one dose of study drug, and with at least one measurement of low dose CT. Analysis will be conducted using As Observed (AO) cases.

Each subject enrolled in the low dose CT sub-study should be measured at baseline, Week 52 and Week 104. The summary of the low dose CT score change from baseline to Week 52 or Week 104 will be summarized by treatment group sequence as defined in section 9.1.1 and the overall group. The descriptive statistics min, max, mean, SD, and the 95% CI of mean for each group at each visit will be provided. The CT scans are evaluated for the full spine (cervical, thoracic, and lumbar spine) by the central image reading and the scoring of the low dose CT Syndesmophyte is described below.

At each timepoint, the reviewer will score a total of 23 vertebral units (VUs), from C2-S1, in the coronal and sagittal planes. In the sagittal view, the anterior and posterior rim of a vertebra can be assessed whereas the left and right rim can be assessed in the coronal view.

By scoring images in the sagittal and coronal planes, 8 quadrants are assessed per VU (i.e., per VU lower and upper borders: coronal - left rim, coronal - right rim, sagittal - anterior rim, and sagittal - posterior rim). With 8 quadrants per vertebral unit, 23 VUs per spine, and a max score of 3 per quadrant, the maximum possible score for a subject is 552 (ACR, 2016, de Bruin, 2017).

A syndesmophyte is defined as a bony spur arising from the vertebral body close to the vertebral endplate in a vertical configuration with an angle of ≥ 45 -degrees in relation to the horizontal endplate. For each quadrant, the reviewer will enter a syndesmophyte score as follows:

0 = no syndesmophyte present

1 = a syndesmophyte is present that does not reach 50% of the intervertebral disc space (IDS)

2 = the syndesmophyte reaches or crosses 50% of the IDS

3 = the syndesmophyte bridges the IDS

A value of 3 is, per definition, scored in both quadrants on opposite sides of the intervertebral disc space. If a VU is not visible (e.g., poor film quality, missing imaging,) at the timepoint, the individual VU will be coded as 'Not Visible' (N). If images at the timepoint show a VU with surgical fusion, then the VU will be scored 'Surgically Modified' (S). No numerical values will be provided for these locations and will be considered as missing.

If a score at any location (vertebral unit) is missing, the method described below will be used for deriving syndesmophyte score.

- If the score for a location is missing at Baseline, this location will not contribute to the calculation of total syndesmophyte score for this subject at any visit within the reading session (even if the score for this location is available at postbaseline visits).
- If the score for a location is missing at all post-baseline visits within a reading session, this location will not contribute to the calculation of total syndesmophyte score for this subject at any visit within the reading session (even if the score for this location is available at Baseline).
- If the score for a location is available at Baseline and at least one postbaseline visit, missing scores for this location at any other post-baseline visit will be imputed assuming no progression from the previous time point with available score.
